8. *Feelings about genomic testing*: Feelings About genomic Testing Results (FACToR) Questionnaire [Time Frame: Baseline, post-disclosure (3 months after enrollment), 6 months post-disclosure (9 months after enrollment)]

Other Pre-specified Outcome Measures:

MDR-associated intervention: Healthcare intervention prompted by monogenic disease risk or recessive carrier variant [Time Frame: 1-year post-disclosure (15 months after enrollment)]

9. *Suspected genetic condition*: Any phenotype that develops in an infant suspected to have a genetic cause, or any genetic testing ordered as part of clinical care [Time Frame: 1-year post-disclosure (15 months after enrollment)]
10. *Cost of attributable services*: Cost of healthcare services that were recommended for infants and parents/guardians as part of study disclosure session [Time Frame: 1-year post-disclosure (15 months after enrollment)]
11. *Cost of genomic services*: Cost of genetic services infants and parents/guardians received after study disclosure session [Time Frame: 1-year post-disclosure (15 months after enrollment)]
12. *All healthcare costs*: All health sector costs observed in medical records and survey questions regarding family out-of-pocket expenses [Time Frame: 1-year post-disclosure (15 months after enrollment)]

5. Data Collection Methods, Assessments, Interventions and Schedule (what assessments performed, how often)

Visit 1 (may occur in multiple parts, remote or in person): Eligibility, consent, demographics, medical history (diagnoses, visits, tests, procedures, medications, hospitalizations, surgeries), family history, baseline parent survey, sample collection

[figure not shown]
Visit 2 (3-4 months after Visit 1- remote or in person): Genome results (for sequencing intervention group), updated medical history, updated medical history, physical exam, post-disclosure parent surveys. Log clinical disclosure note as PDF.

Visit 3 (6 months after Visit 2- remote): 6-month post-disclosure parent survey.

Visit 4 (1 year after Visit 2- remote): Updated participant medical history. Parent(s) medical visits and/or testing (due to study information), and parental records relevant to reproductive decision-making. Document whether each data point is related to genome findings and estimate any associated costs.

Repeat Visit 4 procedures on an annual basis throughout the study period.

6. Study Timeline (as applicable)

E. Adverse Event Criteria and Reporting Procedures

If a participant expresses emotional distress related to study participation or provides survey responses suggesting impaired family bonding or emotional distress, they will be referred to a study physician or study psychologist for further psychosocial assessment as described above. All serious such cases, including those requiring a referral to mental health professional or other therapeutic intervention, will be reported to the IRB as per the current IRB reporting guidelines and at the annual continuing review for the protocol.

F. Data Management Methods

Participant and outcomes data collected as part of this research study will be entered into REDCap: a secure, HIPAA-compliant software hosted inside the coordinating institution firewall (BWH). An experienced data manager will build this database. Each recruitment site will enter identifiable data about participants that cannot be viewed by other recruitment sites. Participant surveys will also be administered through REDCap. Study team members at the coordinating site will have access to all data entered, as needed for recruitment coordination, data monitoring and quality assurance.

Any identifiable data exports from REDCap will be kept in locked cabinets, or in password protected computer files stored securely on institutional HIPAA-compliant platforms. Identifiable data will be kept to the minimum necessary and only included if required for specific analyses. Recruitment sites will never have access to identifiable data from other sites. Teams involved with analysis of psychosocial survey data will not have access to identifiable data unless needed to coordinate interviews. Teams involved with analysis of medical and economic data will have access to identifiable data for analysis of medical records and healthcare claims.

The Laboratory for Molecular Medicine will receive biological samples and store data according to their secure HIPAA-compliant procedures.

All reports placed in the medical records of participating infants will be subject to all privacy protections afforded clinical information.

When genomic data are uploaded to dbGaP and/or other databases for sharing with qualified research investigators, no PHI information will be uploaded that could lead to the identification of these research participants. However, since genome data is a unique dataset (like fingerprints or retinal scans), and since advanced computational techniques may allow deductions with other publically available datasets, it is unlikely but may be possible in the future for individuals to identify research participants through these datasets. This possibility will be discussed in the Pre-enrollment Sessions and in the consent process. We will obtain a Certificate of Confidentiality as another layer of confidentiality protection for participants in this study.

G. Quality Control Method

Research assistants at each site will be trained on data entry methods prior to beginning recruitment. At each recruitment site, one study team member will enter data, and another will cross-check each record until they are confident in accuracy and consistency. After this time, records will be cross-checked as needed. The coordinating site will have access to all data entry and will review regularly and raise queries as needed.

Laboratory quality control will be implemented according to current CLIA- approved methods.

H. Data Analysis Plan

Aim 2a: To assess the psychosocial impact of infant GS on parents/guardians from varying ethnic and racial backgrounds, we will conduct longitudinal surveys and compare validated scales between arms of the RCT.

Aim 3: Exploratory Aim: To evaluate healthcare utilization and associated costs of GS. Using novel approaches, we will identify healthcare services motivated by the study in the two study arms and examine attributable healthcare costs accrued for the infants and other family members.

Since standards have not been established about what to report from GS, we will collect data to conduct one-way scenario analyses that provide insight about reporting strategies that vary the following:

- *Definition of attributable services.* To provide a high side estimate of care that may have been prompted, we will use genomic references, including GeneReviews, OMIM, and primary literature,^{136; 137} to identify all possible follow-up services that may be used to screen for conditions identified on the FHR or NGSR.
- *Classes of findings reported* (e.g., reporting only findings from an IBA, or only MDR).
- *Conditions reported* (e.g., if we reported findings associated only with pediatric-onset conditions, or conditions on the ACMG SF v3.0 list¹¹⁸).
- *Classification criteria* (e.g., if we reported only variants classified as pathogenic)

Intervention costs will include pre-analytics, such as DNA extraction, GS variant classification, and disclosure of results. Post-disclosure costs will use actual cost data when available, updated to the year of analysis using the medical care component of the Consumer Price Index (CPI).^{137; 138} Costs will be assigned to other downstream healthcare services by multiplying utilization by cost weights derived from the Centers for Medicare and Medicaid Studies fee schedules.⁶³ To facilitate analyses from the societal perspective, we will collect data about family out-of-pocket expenses using survey items.^{63; 132} We will use generalized linear models with a log link and gamma family error to compare randomization arms on attributable costs for infants and their parents/guardians. We will also run regression models that include terms for ethnicity and ethnicity-randomization arm interactions to determine whether costs overall and/or incremental cost of GS varies by ethnicity.

I. Statistical Power and Sample Considerations

Aim 2a:

Based on 1-sided t-tests and non-inferiority bounds of 5 points for the GAD-7, 9 points for the PSI-4 (0.5 sd), and 1.1 points for the Kansas Marital Satisfaction scale (0.5 sd) and assuming complete data from at least 200 (an 80% completion rate) families in each randomization arm, we estimate over 99% power to confirm noninferiority of GS on each measure at $\alpha = 0.016$ (after Bonferroni correction for three outcomes). Actual analyses will probably be even more precise due to the use of repeated measures and imputation of missing data. Also, for a correlation of about 0.5 among repeated observations in the same subject (as observed on multiple outcomes during BabySeq), we find that the sample size needed with 3 observations, compared to a single observation, is about 65% for the same power and alpha levels. We will also run separate regression models that include terms for ethnicity and ethnicity-randomization arm interactions to determine whether outcomes vary by ethnicity and whether any impact of GS varied by ethnicity. Our Stakeholder Board will be encouraged to pose additional questions for analysis, review and present results, and co-author publications.

Aim 3:

We will use generalized linear models with a log link and gamma family error to compare randomization arms on attributable costs for infants. Cost analyses will be exploratory, but we anticipate that we will have 93% power at $\alpha=0.05$ (two-tailed) to detect a standardized effect size of $d=0.31$, which is roughly equivalent to attributable costs in the GS arm being approximately 61% greater than attributable costs in the control arm.

J. Study Organization

Boston Children's Hospital

[name], MPH (mPI)

[name] (Co-I)

[name], MPH (Co-I)

Brigham and Women's Hospital

[name], MPH (Contact PI and mPI)

Harvard Pilgrim Health Care

[name] (Co-I)

Icahn School of Medicine at Mount Sinai

[name] (Co-I)

[name], MPH (Co-I)

University of Alabama at Birmingham

[name] (Co-I)

[name], PhD (Co-I)

Laboratory for Molecular Medicine

[name] (Co-I)

[name] (Co-I)

[name] (Co-I)

Baylor College of Medicine

[name], JD, PhD (Co-I)

[name] (Co-I)

HudsonAlpha Institute for Biotechnology

[name], MS (Co-I)

[name] (Co-I)

K. References

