Healthcare Utilization/Cost Outcomes: We explored healthcare utilization and costs using techniques developed and piloted in our prior projects.^{21; 33; 63; 64} Data collected through the parental surveys and medical record reviews captured medical costs and parental time lost from work, and we reviewed the notes from the disclosure sessions. For those in the GS arm recommendations were frequently made for follow-up and testing for the newborn and a family member (Figure 3). Preliminary analyses of total healthcare spending in the 3-months following disclosure (Figure 4) showed that total costs per newborn were higher in the GS (\$567) compared to control arm (\$352).⁶⁵

[figure not shown]

Figure 3. Percentage of BabySeq1 families who received recommendations for clinical follow-up at disclosure or genetic testing in the 10 months following disclosure

[figure not shown]

Figure 4. BabySeq1 total health sector expenditures in the 3 months following disclosure sessions.

Prior Work and Data: Engaging Diverse Populations in Genetic Research

All 3 of the sites bring extensive experience in engaging URM s in genomic research and in addressing mistrust, fear, stigma, and distress within URM communities, including through the All of Us Research Program (AoURP), the Clinical Sequencing Evidence-Generating Research (CSER) Consortium, and the Implementing GeNomics In pracTicE (IGNITE) Network.

In Boston, [name] has led NIH-funded collaborations that have explored URM issues related to genetic testing,⁶⁶⁻⁷³ and consistently recruited 15-24% URM participants in some of the earliest trials disclosing genetic risk information.⁷⁴⁻⁷⁷ [name] also leads an NIH grant that is the first to systematically return genomic results to AA participants in the Jackson Heart Study, as presaged by these early data.⁷⁸

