1b.5. Data collected at enrollment

Demographics and other study intake information will be recorded in a secure REDCap database accessible only to the clinical study team.

A 3-generation family history will be obtained by the research assistant at this stage of enrollment using a standardized template with scripted questions. The family history will be utilized later by the laboratory and the consultation team in the interpretation and contextualization of the sequencing report as well as to create a family history report (FHR) for the family (see attached "Sample FHR"). In the event that the family history suggests that a more targeted form of genetic testing should be pursued (such as a family history suggestive of Lynch syndrome in the parents), the family will receive additional genetic counseling and may be referred for clinical genetic counseling and/or additional targeted genetic testing for this indication.

Baseline survey. All surveys (i.e., baseline, post-disclosure, and 6-months post-disclosure) may be completed in person, over the phone, or online (via REDCap). Participants will be offered the option to have an RA read the survey questions and to respond verbally.

1b.6. Randomization

After completion of the baseline survey, infants will be randomized (1:1) to either standard-of-care (family history) or to standard-of-care plus genomic sequencing, divided approximately equally between the 3 sites. Parents will be notified which group their child is part of and whether a sample needs to be collected.

1b.7. Sample collection

Infants randomized to the sequencing group will have a sample collected for GS. Infants randomized to the control group will not have a sample taken. Sample collection will take place in the clinic by clinical staff or trained research personnel. A blood sample (through a heel stick, finger stick, or venipuncture) of less than 1.0 ml will be obtained from all infants randomized to the genomic sequencing arm. Alternatively, and when possible, leftover blood and/or cord blood samples already obtained may be retrieved, a saliva or buccal swab may be collected. In the case that the sample for an infant does not yield enough DNA for sequencing, we would offer a second sample collection should they agree to this. These samples will be shipped to the Laboratory for Molecular Medicine (LMM) or other CLIA compliant clinical diagnostic facility.

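### The main Aim 3 cost comparison names no baseline covariate, although site, infant age, family history and the infant's medical history are available at baseline in both arms; some precision may be given up.

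*Combined protocol and SAP*

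**What the plan says.** Section H, Aim 3 compares the arms with "generalized linear models with a log link and gamma family error to compare randomization arms on attributable costs for infants and their parents/guardians". Section I, Aim 3 repeats the model for infants' costs. Neither place names a covariate for this comparison. Ethnicity appears only in additional models: "We will also run regression models that include terms for ethnicity and ethnicity-randomization arm interactions to determine whether costs overall" or the incremental cost of sequencing differ by ethnicity. The Aim 2a model in section H, by contrast, does include the baseline value of the outcome.

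Several baseline variables are available:

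- **Family history.** Section 1b.5: "A 3-generation family history will be obtained by the research assistant at this stage of enrollment using a standardized template with scripted questions".
- **Medical history.** Section D.5 lists at Visit 1 "medical history (diagnoses, visits, tests, procedures, medications, hospitalizations, surgeries), family history, baseline parent survey".
- **Timing.** Section 1b.7 says that the baseline survey and data are collected before randomisation.
- **Site and age.** Both are known at enrolment, which is open from 0 to 12 months of age at three sites.

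On power, section I, Aim 3 states: "Cost analyses will be exploratory, but we anticipate that we will have 93% power" at two-tailed alpha 0.05 for d = 0.31. It equates this to "attributable costs in the GS arm being approximately 61% greater than attributable costs in the control arm".

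**The concern.** Cost data vary widely, and a baseline variable that predicts cost can narrow the interval around the arm ratio at almost no expense. On the plan's own definitions, family history is a plausible predictor of attributable cost. Attributable services are those recommended at disclosure or reported as prompted by it (Table 3), and the family history report is the only result returned in the FH arm (section 1b.9). That report also goes to the GS arm. Cost levels may differ by site, because utilisation comes mainly from each institution's own data warehouse. Infant age and prior use are more likely to matter for the all-costs analysis, which covers the child only.

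The width of the interval is at stake, and so is the choice of covariates: with none named, they could be chosen after the costs have been seen.

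**Working it through.** **Inputs.** Standardised effect 0.31 and two-sided alpha 0.05 (section I, Aim 3). 500 infants randomised 1:1, hence 250 per arm (Aim 1 and section 1b.6). 80% completion, hence 200 per arm (section I, stated for Aim 2a only). The share of cost variance explained by covariates, R², is not in the documents; 0.05 to 0.30 is an assumed range.

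**Step 1: the plan's own figure.** Power = Φ(d·√(n/2) − 1.96).

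- n = 250: 0.31 × √125 = 3.466; Φ(1.506) = 93.4%. The stated 93% reproduces.
- n = 200: 0.31 × √100 = 3.10; Φ(1.14) = 87.3%. It does not reproduce.

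The stated power is therefore that of an unadjusted comparison with cost data on all 500 infants. The 61% matches 567/352 = 1.611, from section C, where "total costs per newborn were higher in the GS" arm of the earlier trial. The plan does not say that this is its source.

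**Step 2: with covariates.** Replace d by d/√(1 − R²).

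| Assumed R² | Standard error reduced by | Power, 250 per arm | Power, 200 per arm |
|---|---|---|---|
| 0 | 0 | 93.4% | 87.3% |
| 0.05 | 2.5% | 94.5% | 88.9% |
| 0.10 | 5.1% | 95.5% | 90.5% |
| 0.20 | 10.6% | 97.2% | 93.4% |
| 0.30 | 16.3% | 98.5% | 96.0% |

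An R² of 0.20 makes 200 per arm worth 200/0.80 = 250 per arm.

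**Step 3: check in the planned model.** Gamma log-link models were simulated with 600 runs per scenario, robust standard errors and a coefficient of variation of ln(1.61)/0.31 = 1.54. The covariate had the same proportional effect in both arms. At R² = 0.10 and 200 per arm, power rose from 87.5% to 94.7%, somewhat more than the formula gives. The log ratio was about 0.48 with and without adjustment. A covariate unrelated to cost brought no gain.

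**Step 4: when the covariate's proportional effect differs by arm.** Suppose a family-history condition adds a fixed 500 to cost in both arms, sequencing adds a fixed amount, and the true ratio of mean costs is 1.61. All amounts here are assumptions. Take a base cost of 200 and 10% of families with a condition:

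- FH-arm mean: 200 + 0.10 × 500 = 250. Sequencing adds 0.61 × 250 = 152.5.
- Ratio without a condition: 352.5/200 = 1.76. Ratio with one: 852.5/700 = 1.22.
- Solving the population score equations of a main-effects gamma log-link model gives an arm ratio of 1.70, not 1.61.

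With a base of 100 and 30% of families affected, the same calculation gives 2.05. Across bases of 100 to 200 and 10% to 30% affected, the range is 1.70 to 2.05.

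An arm-by-family-history term fits all four cell means. Averaging the fitted costs over all families then restores the overall ratio: (0.9 × 352.5 + 0.1 × 852.5)/(0.9 × 200 + 0.1 × 700) = 402.5/250 = 1.61.

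**The case against.** The strongest case against is that the plan is silent rather than wrong. It names a model family, does not rule out covariates, and labels the aim exploratory with a stated power of 93%. That stands. A reader might infer that the sponsor has decided to analyse arm alone; the text does not say so.

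Other limits also stand:

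- **Size of the gain.** No R² is given. In the GS arm, attributable services also follow sequencing results (in the earlier trial 18 of 159 infants had a monogenic disease risk and 140 of 159 were carriers, section C). Baseline data may predict these poorly.
- **The 200 per arm.** This is the Aim 2a completion figure. Utilisation data come mainly from institutional data warehouses, so survey drop-out need not carry over. A reader might infer that Aim 3 is underpowered at 87.3%; the documents do not establish that.
- **Prior use.** A reader might infer that prior use is recorded for the whole family. Visit 1 appears to describe the infant's history, and no baseline use by parents is described. Infants enrolled near birth have little prior use. No arm-comparison model is stated for all costs.
- **Timing.** Visit 1 may occur in parts and includes sample collection, which follows randomisation. That the medical history precedes randomisation rests on the general statement in section 1b.7.
- **Chance imbalance.** Under randomisation it is already reflected in the standard error. It is not bias.
- **Risk in adjusting.** Step 4 shows that simply adding family history as a main effect can change what the arm coefficient estimates.

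None of this removes the case for naming covariates in advance. It limits the claim and shapes the remedy.

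**Conclusion.** The point holds as a modest improvement. The main Aim 3 comparison names no baseline covariate, while plausible ones are available in both arms. The gain cannot be computed from the documents. For an assumed R² of 0.05 to 0.30 it is about 1 to 5 percentage points of power at 250 per arm and about 2 to 9 points at 200 per arm. The benefit that matters in an exploratory analysis is the narrower interval: 2.5% to 16.3% over the same assumed range.

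Two stronger conclusions are not supported: that the unadjusted comparison is invalid, and that covariates can be added without care. The first fails because randomisation protects the unadjusted ratio, the second because of the shift from 1.61 to between 1.70 and 2.05 under the assumptions of step 4. Confidence is high that no covariate is named and moderate on the size of the gain.

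**What to change.** In section H, Aim 3, pre-specify:

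1. **Attributable costs:** site, infant age, and a yes/no family-history flag coded from the baseline template by someone blind to arm.
2. **Any arm comparison of all costs:** the same covariates plus the infant's prior visits and hospitalisations, restricted to events before randomisation.
3. **Model and estimate:** keep the gamma log-link model and add the arm-by-family-history term. Predict each family's cost under both arms, average, and report the ratio of the two means with robust or bootstrap standard errors.
4. **Comparison:** report the unadjusted ratio beside it. Site and age enter as main effects, so a marked gap between the two ratios would call for explanation.

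The cost is a short paragraph in the plan, a coding rule for the flag and slightly more analysis work. The rule is new: section 1b.5 describes the history and its later use in the family history report, but no such flag. No new data collection is needed, provided that the medical-history items can be dated relative to randomisation.

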In the event that one of the babies becomes ill with symptoms where a genomic analysis may be helpful for diagnosis or treatment of a particular presentation, an “Indication-Based Analysis” (IBA) will be generated in response to requests by the baby’s physicians in consultation with the study team, or by the study team physicians. The IBA will include interrogation of genes associated with the syndrome or clinical features in question, as currently practiced in medical genetics. In addition, upon request, an IBA may additionally include Evidence Class I and II variants from PharmGKB¹¹⁹ for specific indications (e.g., anti-epileptic medication in neonates with seizures). For every situation in which an IBA is requested, the study physician will be in communication with the clinical team or physician ordering the IBA and will make sure that a re-query of the genomic sequence is not ordered in lieu of a targeted genetic test or panel that would be more appropriate for a specific presentation. Gene-disease criteria for the IBA will include results in genes that have a moderate level of evidence (using the ClinGen framework). Penetrance will not be considered in reporting as these individuals will be exhibiting symptoms. The IBA will include variants that are considered Variants of Uncertain Significance (VUSs) relevant to the condition, according to the ACMG/AMP criteria in addition to pathogenic and likely pathogenic variants.

1b.9 Consultation and Disclosure of Reports

A study physician and/or genetic counselor will disclose study results during a consultation with each family held either in-person, by video, or by phone. The study physician/genetic counselor will provide the consultation to families utilizing all available medical information. For Spanish-speaking families, the session will be completed in Spanish with a professional interpreter and the reports will be in Spanish.

Both arms: The review of the family history report will be returned. If the family history obtained during the baseline visit suggests that targeted genetic testing for a Mendelian condition should be pursued, the family will receive additional genetic counseling, and may be referred for clinical genetic counseling and/or targeted testing for this indication. For the FH arm, this is the only result that will be returned

Figure 8. Workflow for Infants and Parents

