Primary analyses of healthcare utilization and costs will expand an “attributable services” approach implemented in related work we have conducted.^{56; 63} We will use the notes from disclosure sessions to identify services that were recommended for infants or parents/guardians, and then verify whether the services occurred. By including only services that we can link directly to this study, this approach will produce data with the greatest measurement precision. To identify efficiencies where genetic tests were avoided by having GS, and to identify instances of cascade genetic testing, we will also focus on genetic services that infants and parents/guardians received after disclosure sessions. Finally, we will conduct “all costs” analyses where we summarize all health sector costs observed in medical records and supplemented by survey items that ask about hospitalizations, health care visits, genetic services, and familial out-of-pocket expenses. Due to the expansiveness of this approach, “all costs” analyses will focus on costs for the care of the child only.

Data about health care utilization will be obtained from infants’ medical records, primarily from each institution’s corporate data warehouse, and supplemented with participant-reported data from interviews and surveys. Costs for services will be assigned to services based on actual costs, where data is available, or by assigning cost weights using reimbursement rates per the Centers for Medicare and Medicaid Studies.

2. Patient Selection and Inclusion/Exclusion Criteria

Inclusion criteria:

Table 3. Healthcare Utilization Analysis Strategy

Approach	Overview of Services Included	Population of Focus
Attributable services	Services that were recommended during disclosure sessions and services patients reported as motivated by BabySeq disclosure	Child and parents
Genomic services	Any genetic or genomic test	Child and parents
All costs	All healthcare, out-of-pocket, and informal health sector costs	Child only

HCP participants

- a. Age 18 years of age or older
- b. Pediatric health care provider providing primary care to infants in the clinics from which we will enroll (physician, nurse practitioner, physician assistant).

Infant participants

- a. Age 0-12 months
- b. Seen for pediatric care at participating clinic where local clinic champions have completed the GS education program
- c. One parent or guardian meeting the parent/legal guardian inclusion criteria

Parent/Guardian participants

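### Aim 3's gamma-error cost model has no rule for zero costs, and its power sentence leaves the sample size, the spread behind the 61% and the cost unit unsettled (minor, exploratory aim)

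*Combined protocol and SAP*

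**What the plan says.** - **Model and unit.** Section I, Aim 3: "We will use generalized linear models with a log link and gamma family error to compare randomization arms on attributable costs for infants". Section H, Aim 3 gives the same model for a wider unit: "gamma family error to compare randomization arms on attributable costs for infants and their parents/guardians".
- **What counts as attributable.** Section D, Aim 3 takes recommended services from the disclosure notes and checks whether they took place: "By including only services that we can link directly to this study", it expects its best measurement precision. Table 3 defines the category as "Services that were recommended during disclosure sessions and services patients reported as motivated by BabySeq disclosure", for child and parents. The outcome list in Section D.4 has "Cost of healthcare services that were recommended for infants and parents/guardians as part of study disclosure session", at one year after disclosure.
- **Family history arm.** Section 1b.9, on the family history report: "For the FH arm, this is the only result that will be returned".
- **Intervention costs.** Section H, Aim 3: "Intervention costs will include pre-analytics, such as DNA extraction, GS variant classification, and disclosure of results". It does not say whether these enter the modelled variable.
- **Power.** Section I, Aim 3 calls the cost analyses exploratory, then says "we anticipate that we will have 93% power at" two-tailed alpha 0.05 for d = 0.31, described as roughly a 61% excess in attributable cost. It gives no n, loss, SD or CV. Under Aim 2a the same section assumes 200 families per arm (80% completion).

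**The concern.** An infant or family with no study-linked service has an attributable cost of zero. That can happen in both arms, and the text does not give the share. The gamma distribution covers positive values only, so the stated model does not fit the stated outcome, and no section supplies a rule such as quasi-likelihood or a two-part model.

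What is at stake is an undeclared choice at analysis. If the software rejects zeros and the analyst then removes them, the arms are compared only among those who used a service. Use of a service is a post-randomisation event that sequencing may itself change, so any difference in the share receiving follow-up is lost.

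Separately, without a sample size, a spread and one cost unit, a reader cannot tell what excess in attributable cost the trial could detect, or for whom.

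**Working it through.** **1. Zeros.** The gamma log-density contains the term (a − 1)·log y, where a is the shape. As y approaches 0 it goes to −∞ for a = 2 and to +∞ for a = 0.5, so zero costs have no usable likelihood.

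The point estimate is a different matter. With a log link and variance proportional to μ², the estimating equation is Σ x(y − μ)/μ = 0, which is defined at y = 0. With a single arm indicator it returns the ratio of arm means. Example: costs 0, 0, 5, 10 in one arm and 0, 0, 8, 20 in the other give means of 3.75 and 7.00. The statsmodels Gamma(log) coefficient is 0.624, and exp(0.624) = 1.87 = 7.00/3.75; the log-likelihood is reported as infinite.

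On 500 simulated families with zeros inserted at an assumed rate, R's Gamma(log) stopped with an error about non-positive values. R's quasi model (log link, variance μ²) and statsmodels kept all 500.

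Why dropping matters: let p be the share with any cost and m the mean cost among users, with m equal in both arms. The ratio of arm means is p(GS)/p(FH). After zeros are dropped it is m/m = 1, whatever the true ratio.

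**2. The 93%.** Inputs: d = 0.31 and two-sided alpha 0.05 (Section I); 500 infants (Aim 1) at 1:1 (Section 1b.6), so 250 per arm. Normal approximation: power = Φ(d·√(n/2) − 1.96).

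- n = 250: 0.31 × 11.18 − 1.96 = 1.51, giving 93.4%; noncentral t gives 93.3%. The stated figure is reproduced.
- n = 242: 92.6% (t).
- n = 200: 0.31 × 10 − 1.96 = 1.14, giving 87.3%; t gives 87.1%.

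So 93% needs almost every infant to contribute. The 200 is the Aim 2a figure, borrowed here as an assumption.

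**3. The 61%.** Section C reports 567 and 352 dollars per newborn as total spending in the 3 months after disclosure: 567/352 = 1.611. Turning d = 0.31 into a ratio of 1.611 requires a CV, and the CV depends on how d is defined, which the plan does not say:

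- control-arm SD: 0.611/0.31 = 1.97
- log ratio divided by CV: ln(1.611)/0.31 = 1.54
- pooled SD, common CV: 0.611/(0.31 × √((1 + 1.611²)/2)) = 1.47

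Across these three definitions, the ratio equivalent to d = 0.31 at assumed CVs is:

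| CV | Ratio |
|---|---|
| 1 | 1.31 to 1.37 |
| 1.5 | 1.46 to 1.63 |
| 2 | 1.62 to 1.97 |
| 3 | 1.93 to 3.21 |

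For the planned log-link model with a common CV, Wald power for a ratio of 1.61 is Φ(ln 1.61/(CV·√(2/n)) − 1.96). At n = 250:

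- CV 1.54: about 93%
- CV 1.97: 0.476/(1.97 × 0.0894) − 1.96 = 0.74, giving 77%

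The CV of 1.97, which makes 61% equal to d = 0.31 on the control-SD reading, therefore does not give 93% in the model the plan names.

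**4. Unit.** Section H, Table 3 and the Section D.4 outcome all cover infants and parents/guardians. Section I covers infants only.

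**The case against.** The best defence is that little would go wrong in practice. The gamma estimating equation works with zeros kept and gives the same estimate as the model proposed below. A two-part model would also be acceptable. The n can be recovered from the enrolment target, the 61% is offered only as a rough equivalence, and infants are a subset of the wider unit, so Section I may simply describe the infant component. The aim is exploratory throughout. All of this stands, and it is why the point is minor.

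A reader might infer more than the documents support:

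- **That zero-cost families will be dropped, or that the model cannot be fitted.** No section proposes dropping them, and some software fits the model with zeros kept. The gap is that the plan is silent.
- **That the 93% is an arithmetic error, or that true power is 87%.** It reproduces at 250 per arm. The 80% completion rate belongs to the Aim 2a surveys. Costs come mainly from institutional records, and consent covers billing data, so loss may be smaller.
- **That the 61% was taken from the earlier study.** The ratios match, but the plan does not state the link.
- **That intervention costs certainly leave the zeros in place.** Disclosure happens in both arms, so adding its cost would remove them. Table 3 and the outcome definition do not list intervention costs, but Section H does not say they are excluded.

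**Conclusion.** The point holds as a minor specification gap in an exploratory aim. The named likelihood is not valid for values that the outcome, as defined, can take in either arm, and no rule is given. No size of bias is claimed, because the share of zeros is unknown and the bias arises only if zeros are dropped. The 93% is correct for a two-sample t-test at d = 0.31 with no loss; 87% applies if 200 per arm contribute, which is an assumption. The 61% cannot be checked without a CV: in the log-link model it goes with 93% power at a CV of about 1.54 but with about 77% at 1.97, assuming the same CV in both arms. The figure it matches is total cost over 3 months, whereas the Aim 3 outcome is attributable cost at one year. Sections H and I name different units and need to be reconciled.

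**What to change.** 1. In Sections H and I name one unit (infants and parents/guardians, as in Table 3 and the outcome list), or state that the Section I figure covers the infant component only. Then add: *All randomised units with cost data are included, at zero cost if no study-linked service occurred. Arms are compared by the ratio of mean costs from a log-link model with variance proportional to the squared mean and robust standard errors. Intervention costs are excluded from this outcome.* Also say whether families who never attended disclosure count as zero or as missing, since recommended services are read from disclosure notes.
2. Restate the power: *Two-sample t-test approximation, d = 0.31, two-sided 0.05: 93% if all 250 per arm contribute; 87% with 200 per arm (the Aim 2a completion rate, used here as an assumption).*
3. Delete the 61% equivalence, or give its SD or CV, its source and the definition of d. If it is the earlier study's ratio, label it as 3-month total cost per newborn.

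The cost is a few sentences of text, slightly more analysis work and a less favourable stated power. A quasi-likelihood fit gives no AIC or ordinary likelihood-ratio test. No new data are needed.
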